## **Procedures**

OB smokers (n=60) will be randomized to either a combined self-regulation plus large changes (SR) intervention in advance of smoking cessation treatment condition (n=30) or to a healthy lifestyle education (LE) in advance of smoking cessation treatment attention-placebo control condition (n=30) for 16 weeks. The study will include up to 18 groups each run in succession with approximately 4-6 participants recruited for each group in order to have 3-5 participants beginning each group. Groups will be randomly assigned to one of the two treatment conditions using a random number generator after participants have completed all pretreatment assessments. Participants will learn their condition assignment at the first treatment session. Feasibility and acceptability will be monitored. Assessment of smoking/abstinence and weight will be obtained at baseline, on Quit Day, and 1, 2, & 3-months post-quit.

Recruitment procedures- Participants will be recruited through print and electronic advertising (e.g., newspaper, magazine, listserv, websites, online ads), advertisements on buses or at bus stops, and via community outreach (e.g., providing study information and pamphlets to local physicians).

Initial screening: Interested individuals will be given several options for contacting the study and for completing initial eligibility screening depending on advertising modality (e.g., call the study telephone number, email the study email address, provide their contact information in an electronic interest form). Individuals will be given the option of either completing initial screening using an online screener or being contacted by study staff for telephone screening.

Phone screening: Individuals who are screened over the telephone will be contacted by study staff. They will be provided with a brief description of the study, and will be asked if they are interested in participating. Verbal consent will be obtained prior to the potential participant's completion of the phone screen using a bulleted consent form that includes key information. Individuals who indicate that they would like a copy of the consent document will be provided a copy via email.

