Screening at baseline: 1. Height and weight to calculate BMI. 2. Screening interview- Age, number of cigarettes per day for past year, use other nicotine or tobacco products, current smoking cessation or weight loss treatment/medication. 3. Medical conditions and medications screening tool will be used to screen for recent medical, substance-related, or psychiatric hospitalizations and any medical conditions or medications that warrant exclusion for safety (determined by PI and study Medical Monitor). 4. Participants will complete questionnaires to assess for symptoms of disordered eating (Eating Disorders Assessment (EDA), severe depression or suicidality (total score  $\geq 20$  or question 9 score  $\geq 1$  on the Patient Health Questionnaire 9-item depression index (PHQ-9), reviewed by clinician), or substance or alcohol use disorders (CAGE-AID score  $\geq 2$ , reflecting past 6 months). 5. Salivary cotinine and/or exhaled carbon monoxide (CO) to confirm smoking status.

Feasibility. In order to quantify feasibility of recruitment and enrollment during pilot testing the number of participants screened and enrolled will be documented per month during periods of active recruitment. The proportion of enrolled participants completing planned assessment sessions will be calculated.

Acceptability. Treatment attendance- Attendance at all counseling sessions will be recorded. Percentage of participants completing each treatment session will be calculated to examine treatment-specific retention rates. Participant Feedback- Participants will complete brief assessments at weeks 9 & the end of treatment (month 2) to assess: 1) helpfulness of interventionist, 2) perceived clinical usefulness, 3) personal relevance, 4) level of engagement, and 5) overall satisfaction scored 1 (not at all) to 5 (extremely) on a Likert-scale. Data on acceptability of other aspects of intervention (e.g., group component, pre-quit NRT, nicotine patches, nicotine lozenges, and smoking text messages) will also be assessed using a 5-point Likert scale. Participants will also be asked to provide brief feedback on sessions after each session.

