#### Data Analysis Plan

Feasibility & Acceptability. Average monthly number of individuals screened and enrolled will show feasibility of screening and recruitment. The proportion of participants completing the final study assessment will show feasibility of retention. Response to SR & LE conditions. Attendance. The percentage of treatment sessions attended through week 10 (one week post-quit) will be calculated and compared between conditions; average attendance of  $\geq$  70% in both arms suggests good acceptability. Participant Feedback. Participant ratings of intervention satisfaction mean scores  $\geq$  3.5 (5-point scale) shows acceptability in each condition.

Intervention effects on treatment outcome variables: Based on ITT principles, all assigned participants will be used in analyses regardless of adherence and missing data. Participants with missing data will be assumed to have smoked and to have regained 0.3 kg/month (positive imputation) and analyses will be repeated using multiple imputation for sensitivity analyses. Generalized estimating equations (GEE) Group x Time analyses will be used for weight change and abstinence. Abstinence. The dependent variable of 7-day point-prevalence abstinence will be analyzed by time (Quit Day, 1, 2, 3-months post-quit) and conditions. Weight. The dependent variable of weight, will be analyzed by time (baseline, Quit Day, 1, 2, 3- months post-quit) and conditions. Secondary exploratory analyses will repeat the GEE analyses adding sex as a variable, and (separately) adding any/no weight loss at week 9 as a variable in predicting smoking abstinence.

Putative mechanisms will be examined using regression analyses to test the effects of treatment on proposed mechanistic variables at week 9, controlling for baseline values. Regression analyses will also test the effects of these proposed mechanisms on follow-up smoking outcomes. Notably, detection of statistically significant effects is not an objective in this limited-powered study.

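### Does the 70% attendance criterion fail because the plan does not say whose attendance is averaged?

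*Combined protocol and SAP*

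**What the plan says.** The acceptability part of the Data Analysis Plan defines the measure as follows: "The percentage of treatment sessions attended through week 10 (one week post-quit) will be calculated and compared between conditions". The benchmark is average attendance of at least "70% in both arms suggests good acceptability". No set of participants is named.

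Three other places bear on the base:

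- **Procedures, recruitment and assignment.** The plan is for "approximately 4-6 participants recruited for each group in order to have 3-5 participants beginning each group". On assignment it says: "Groups will be randomly assigned to one of the two treatment conditions using a random number generator after participants have completed all pretreatment assessments". It adds: "Participants will learn their condition assignment at the first treatment session". The same section gives 60 smokers to be randomized, 30 per condition.
- **Procedures, Feasibility paragraph.** Here a base is named, but for assessments and not for treatment sessions: "The proportion of enrolled participants completing planned assessment sessions will be calculated".
- **Data Analysis Plan, intervention effects.** "Based on ITT principles, all assigned participants will be used in analyses regardless of adherence and missing data". This sentence comes after the attendance criterion, under the heading for the treatment outcome variables.

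**The concern.** A percentage criterion with no stated base can give two answers from one set of records. The protocol makes this possible. It expects some recruited people not to begin. It assigns whole groups once the pretreatment assessments are done, and it discloses the condition only at session 1. Someone can therefore be assessed, assigned with the group and never appear. Over all assigned, that person contributes zero attendance; over those who begin, that person is not counted.

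Acceptability is part of the study's stated aim, and this is one of two numeric acceptability thresholds (the other is a mean satisfaction rating of at least 3.5). If the base were chosen after the data were seen, the same attendance could be reported as meeting or missing the benchmark. Because both arms must pass, a switch in one arm would be enough.

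**Working it through.** The 70% is a chosen benchmark with no derivation, so there is no figure of the plan's own to reproduce. The check is how far the two bases can differ.

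**Inputs**
- Threshold: 70% in each arm (Data Analysis Plan).
- Sessions counted: 10, one per week through week 10 (16 weekly sessions, Interventions).
- Assigned per arm: 30 (Procedures). Person-sessions per arm: 30 × 10 = 300; needed to pass: 0.70 × 300 = 210.
- Share of assigned participants who never start, d: **not given**. The recruitment ranges concern loss from recruited to beginning. Pairing 6 with 5, 5 with 4 and 4 with 3 gives 1/6, 1/5 and 1/4. That pairing is an assumption, since both ranges are approximate. Treating all of that loss as occurring after assignment is a second assumption, and it makes these the upper end.

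**Formula.** Attendance over all assigned = attendance among starters × (1 − d).

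| d (assumed) | 70% among starters becomes | Starter attendance needed for 70% over all assigned |
|---|---|---|
| 0 (all loss before assignment) | 70.0% | 70.0% |
| 1/6 | 0.70 × 5/6 = 58.3% | 0.70 ÷ 5/6 = 84.0% |
| 1/5 | 0.70 × 4/5 = 56.0% | 0.70 ÷ 4/5 = 87.5% |
| 1/4 | 0.70 × 3/4 = 52.5% | 0.70 ÷ 3/4 = 93.3% |

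So the verdict depends on the base only when starters average at least 70% but less than the figure in the last column. Below 70%, both bases miss. At or above that figure, both pass.

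**In whole participants.** With starters at 80% (8 of 10 sessions on average) in an arm of 30:
- 3 never-starters: 27 × 8 = 216; 216/300 = 72.0%, met.
- 4 never-starters: 26 × 8 = 208; 208/300 = 69.3%, missed.

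The smallest number of never-starters in an arm of 30 that takes the all-assigned average below 70% is 3, 4, 6 or 7 when starters average 75%, 80%, 85% or 90%.

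**When the loss is likely to occur.** Recruitment is followed by an orientation session, consent, baseline assessment and a wait until a group is full. Assignment comes only after the pretreatment assessments. People lost during those steps belong to no arm and enter neither average. The documents do not divide the expected loss between that period and the interval from assignment to session 1.

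**The case for a change.** The best case for a change is that naming the base costs one sentence, needs no new data and removes a choice that could otherwise be made with the results in view. The sentence about all assigned participants does not strictly settle it, because its heading limits it to the outcome analyses. The Feasibility paragraph also shows that the authors name a base when they think of it. All of this stands: the base is not written down, and stating it would do no harm.

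It does not show that the plan goes wrong. No stated rule produces a false result. Arms most naturally means the randomized arms of 30, which agrees with the principle the same section applies to the outcomes. Nor is there one correct base to impose. The plan treats attendance as a response to the two conditions. A person who never starts has not yet been told the condition, so that absence is not a reaction to either program. Counting it as zero would lower an acceptability figure for a reason other than acceptability, while leaving it out would hide early loss. Each average answers a fair question, and ordinary reporting of numbers assigned, numbers beginning and attendance by arm lets a reader see both.

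**Conclusion.** No change follows. The base for the attendance average is unstated, and the two readings can fall on opposite sides of 70%: at 80% starter attendance in an arm of 30, the fourth never-starter is the one that matters. But the effect ranges from nothing, if all non-starters leave before assignment, to 11.7–17.5 percentage points for starters at exactly 70% (70 − 58.3 and 70 − 52.5), if the whole assumed shortfall of one sixth to one quarter falls after assignment. The documents do not place the trial within that range, and a reversal also requires starter attendance inside the band shown above.

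The consequence is confined to how a pilot describes its acceptability. The benchmark is worded as suggestive, no decision to proceed is tied to it, and the plan says that significance testing is not its objective. Attendance is recorded at all counseling sessions, so either average can be obtained. This is a gap in detail that an analyst fills sensibly by using the randomized arms and showing those who began alongside. The conclusion rests on the criterion remaining descriptive.

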Self-regulation plus large changes in behavior (SR). The active intervention is based on self-regulation theory and is similar to interventions tested previously and shown to be effective in reducing weight gain and weight regain. The initial 8-week program will include weekly group sessions focused on teaching self-regulation and efforts to produce a 10 lb weight loss to buffer against anticipated post-cessation weight gain based on the SR approach. The key concepts of the intervention: Self-Regulation. Participants will be taught the core self-regulation skills for controlling their weight: a) weighing themselves daily; b) detecting small changes in weight as soon as they occur; c) implementing problem-solving skills and learned strategies to combat changes in weight; d) evaluating the success of strategies implemented; e) rewarding themselves for successful weight loss and weight maintenance or f) making behavioral changes if weight gain occurs. These strategies are introduced over the course of the 8 weeks, with the initial weeks stressing the importance of daily self-weighing and learning to use the scale for information (rather than self-evaluation). At the end of the initial 8 weeks, the participants will be introduced to a color-coded system to help them accomplish steps b-f of the self-regulation model. The goal for the first 8 weeks of the program will be to lose 10 lbs in order to buffer against expected weight gain. To accomplish this, participants will be given a reduced calorie goal (1200-1500 kcal/day if <200 lbs or 1500-1800 kcal/day if >200 lbs). They will be instructed to self-monitor their intake and taught strategies for reducing caloric intake (e.g. reducing fat content of foods) and strategies for dealing with high-risk situations such as eating out. Structured physical activity, which is activity similar in intensity to brisk walking that lasts at least 10 minutes, will also be prescribed and self-monitored, starting with a goal of 50 minutes per week (10 minutes per day on 5 days per week) and gradually increasing to 150 minutes per week.

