Weeks 9-16 will focus on smoking cessation, but each session will include a private weigh-in and brief group discussion of strategies to maintain weight loss and prevent post-cessation weight gain. To maintain the weight losses achieved thus far and prevent post-cessation weight gain, participants will be taught to use a color zone system (Red, Yellow, Green) for weight maintenance to guide their behavior after completing the initial 8-week weight control program. The weight goals used to define the zones will be individually tailored based on the initial weight changes. Participants will be encouraged to weigh themselves daily and at the end of each week and to assess their current weight relative to their individual color zones. If participants are in Green, they will be encouraged to reinforce their success (with a sticker or small amount of money); if they are in Yellow they will be taught to begin monitoring their behavior more carefully and identify area to make changes to get back on track; if they are in Red, they will be encouraged to return to full self-monitoring of intake and activity and resume their original calorie intake and goals. During smoking cessation, the goal will be to minimize weight gain for those who achieved targeted weight loss as well as for those who did not. This Red, Yellow, Green system for weight maintenance has had demonstrable success in prior studies of the self-regulation model.

Healthy lifestyle education attention-placebo control (LE). Participants in this group will be provided with information on the obesity epidemic and the importance of a healthy lifestyle to use at their own pace as they wish. They will receive basic education about principles of healthy eating (e.g., simple vs. complex carbohydrates) and physical activity during the first 8 sessions. During sessions 9-16, the focus will be on smoking cessation. Sessions will also include lifestyle education information such as why weight gain occurs after smoking cessation. This group will not be taught any specific behavioral self-regulation skills to help them change their behaviors. Providing basic education about diet and exercise has produced minimal weight loss in other clinical trials.

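### The main weight analysis fills missing weights with a fixed +0.3 kg/month in both arms, which dilutes the effect for early dropouts; the multiple imputation already planned should be primary for weight

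*Combined protocol and SAP*

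**What the plan says.** All references are to the combined protocol and SAP.

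The Data Analysis Plan follows intention to treat: "all assigned participants will be used in analyses regardless of adherence and missing data". Missing outcomes are then filled by one rule: "Participants with missing data will be assumed to have smoked and to have regained 0.3 kg/month (positive imputation". The rule does not distinguish the arms, does not say which weight the monthly gain is added to, and gives no source for 0.3 kg. Multiple imputation has a supporting role: "analyses will be repeated using multiple imputation for sensitivity analyses". No imputation model is given.

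The model is stated as "Generalized estimating equations (GEE) Group x Time analyses will be used for weight change and abstinence", and the visits as "The dependent variable of weight, will be analyzed by time (baseline, Quit Day, 1, 2, 3- months post-quit) and conditions". The sample is 60, split 30 and 30 (Procedures). The Brief Summary and the Specific Aims both name preliminary effect size data as a purpose. The Data Analysis Plan adds that statistical significance is not an objective.

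On expected weight change, Procedures describes SR as "efforts to produce a 10 lb weight loss to buffer against anticipated post-cessation weight gain" over the first 8 weeks, and says of LE-type content: "Providing basic education about diet and exercise has produced minimal weight loss in other clinical trials".

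**The concern.** The arms are expected to differ in weight by Quit Day. A rule that gives dropouts in both arms the same weight change removes that difference for everyone it touches. The GEE then treats the assumed weights as measured, and a robust variance does not restore the uncertainty about what those weights were.

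The SR-LE weight difference, its SD and its confidence interval are what the pilot passes on to the larger trial. If they come from the fixed-fill analysis, part of the headline effect size is set by the rule, by how many people leave and by when they leave. That the pilot does not aim at significance makes the estimate and its precision more important, not less.

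**Working it through.** **Inputs from the documents.** 30 per arm; weights at baseline, Quit Day (week 9, about month 2) and 1, 2 and 3 months later (about months 3, 4 and 5); fill of 0.3 kg/month. The documents state no dropout rate, SD, starting weight for the fill or sample-size calculation, so there is no figure of theirs to reproduce. Everything else below is an assumption.

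**Step 1: lost before Quit Day.** The only assessment weight is baseline, so last weight and baseline are the same starting point. The filled change is f = 0.3 x 2 = +0.6 kg at Quit Day and 0.3 x 5 = +1.5 kg at month 3, in both arms. With a fraction m lost at random in each arm and true mean changes μ_SR and μ_LE:

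expected difference = [(1-m)μ_SR + m f] - [(1-m)μ_LE + m f] = (1-m)(μ_SR - μ_LE)

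The constant cancels and no SD is needed. m = 20% gives 20% dilution; m = 30% gives 30%. If the arms lose different fractions, a further term (m_SR - m_LE)f appears and the two means are shrunk unequally.

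**Step 2: lost after Quit Day.** If the fill starts from baseline, Step 1 applies unchanged. If it starts from the last weight, with k months still to run on average and true monthly gains r_SR and r_LE:

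bias in (SR - LE) = m k (0.3 - r_SR) - m k (0.3 - r_LE) = m k (r_LE - r_SR)

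The 0.3 cancels again. With assumed gains of 0.8 (SR) and 1.0 (LE), k = (3+2+1)/3 = 2 and m = 30%, the bias is 0.3 x 2 x 0.2 = 0.12 kg toward zero. If SR regains faster than LE, the sign reverses and SR is favoured.

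**Step 3: standard error, closed form.** When each missing change score is one constant, the SE relative to observed cases only is (1-m) x sqrt(1 + m g²), where g is the distance from the observed mean to the fill in SD units. For g between 0 and 1:

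- m = 10%: 6-10% smaller
- m = 20%: 12-20% smaller
- m = 30%: 20-30% smaller

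**Step 4: simulation against multiple imputation.** Assumed: mean change to Quit Day -3.5 kg (SR) and -0.5 kg (LE), SD 3 kg; monthly steps with the gains above, SD 1 kg; random dropout that is permanent once it occurs; 20 imputations; 600 trials per row. True month-3 difference = (-3.5 + 0.5) + 3 x (0.8 - 1.0) = -3.6 kg. An ordinary two-sample SE stood in for the GEE, and clustering by treatment group was ignored.

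| Missing | When lost; fill starts from | Fixed-fill estimate, kg | SE fixed / MI | SE smaller by | Coverage fixed / MI |
|---|---|---|---|---|---|
| 10% | all after Quit Day; last weight | -3.62 | 0.890 / 0.902 | 1% | 96% / 97% |
| 10% | all before Quit Day; either | -3.24 | 0.857 / 0.953 | 10% | 93% / 95% |
| 20% | all after; last weight | -3.52 | 0.884 / 0.912 | 3% | 95% / 95% |
| 20% | half before; last weight | -3.15 | 0.854 / 0.963 | 11% | 91% / 95% |
| 20% | all before; either | -2.82 | 0.818 / 1.025 | 20% | 82% / 94% |
| 30% | all after; last weight | -3.50 | 0.880 / 0.932 | 6% | 95% / 96% |
| 30% | all after; baseline | -2.50 | 0.773 / 0.927 | 17% | 70% / 94% |
| 30% | all before; either | -2.55 | 0.784 / 1.122 | 30% | 73% / 95% |

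The estimates agree with Steps 1 and 2: 0.8 x 3.6 = 2.88, 0.7 x 3.6 = 2.52, and 3.6 - 0.12 = 3.48. Multiple imputation gave -3.5 to -3.7 kg throughout.

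**Step 5: the other direction.** A second simulation (30 per arm, change SD 3.0-4.8 kg, 26-31% random dropout) set the true month-3 difference to zero because SR had regained its loss. The last-weight fill then showed a spurious SR benefit of 0.3-0.8 kg.

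**The case against.** **The plan already includes multiple imputation.** Both estimates will exist, in a pilot that disclaims significance. This stands, and it lowers the severity. The remaining issue is which estimate is the headline, and that is best settled before results are seen.

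**The wording suggests gain from a later weight.** Regain reads most naturally as starting from the last observed weight, and on that reading late dropout gives a bias of only about 0.1 kg in Step 4. This also stands. It does not help participants lost before Quit Day, whose last assessment weight is baseline.

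**A reader might infer a fixed understatement of the error bars, such as 19-28%.** The documents do not support one figure: the range is about 1-30% and depends on an unstated dropout rate, its timing and the starting weight. Nor is the fixed-fill SE wrong for its own estimator (0.818 against an empirical spread of 0.843 at 20% lost early). The interval fails because it is tight around a shifted value and leaves out doubt about the missing weights.

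**A reader might infer that the rule is too lenient to SR.** A participant at goal (10 lb = 4.54 kg) who is then lost is given back only 0.3 x 3 = 0.9 kg by month 3, so keeps 1 - 0.9/4.54 = 80% of the loss. But that buffer is set against gain after quitting, while the same rule presumes that people with missing data are smoking. The documents give no gain rate for either group, so they do not show that 0.3 is too low.

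**Multiple imputation is not sound without conditions.** It relies on missing at random and a suitable model. Both simulations used random dropout, which suits it. If people who regain weight are the ones who leave, it too can be biased.

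**Conclusion.** The concern holds in limited form. The main analysis uses one unanchored fixed fill for weight. For participants lost before Quit Day, it shrinks the expected SR-LE difference by the fraction lost; this follows from the rule itself and assumes only similar, random loss in the two arms. For later losses the bias ranges from near nil to substantial and can take either sign, depending on the starting weight and true regain. Under an assumed 10-30% missing, the SE is about 1-30% smaller than under multiple imputation, and in the worst rows coverage falls to 82% (20% missing) and 70% (30% missing).

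The documents do not support saying that the result must be biased by a known amount, or that the pilot cannot proceed as written. This is a cheap improvement, below the level of a required correction. It is worth making because it changes the headline effect size that the pilot is meant to produce.

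**What to change.** In the Data Analysis Plan, for weight only:

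- Make multiple imputation primary, or a likelihood-based repeated-measures model. State the model: condition, all observed weights and abstinence.
- If treatment group is included, enter it as a random effect. Whole groups of 3-5 are assigned to a condition (Procedures), so fixed group indicators would be collinear with condition.
- Keep +0.3 kg/month as a sensitivity analysis, and state its starting weight and its basis.
- Counting missing as smoking may stay as the abstinence convention.

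Both weight analyses are already planned, so the cost is mainly in the text, plus specifying an imputation model that 60 participants can support. The weight interval will be wider: 1.40/1.17 to 1.43/1.02, or about 20-40%, in the second simulation at 26-31% dropout. In the Step 4 table it runs from about 1% (0.902/0.890, low and late loss) to 43% (1.122/0.784, 30% all lost early). The primary result will also rest on missing at random, which the retained fixed-fill analysis helps to probe.

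### The plan names a GEE for weight but gives no clustering unit, variance estimator or small-sample method, although only about 12-18 treatment groups are randomized

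*Combined protocol and SAP*

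**What the plan says.** The Data Analysis Plan gives the between-condition model in one sentence: "Generalized estimating equations (GEE) Group x Time analyses will be used for weight change and abstinence". For weight it adds: "The dependent variable of weight, will be analyzed by time (baseline, Quit Day, 1, 2, 3- months post-quit) and conditions". That makes five time points. The section does not say whether time is categorical or linear. It is also silent on the working correlation, the clustering unit, the variance estimator, the reference distribution and any small-sample correction. It sets no significance level, and it states that finding significant effects is not an aim.

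Procedures first describes 60 smokers randomized to two conditions with 30 in each, and then describes allocation of whole groups: "Groups will be randomly assigned to one of the two treatment conditions using a random number generator after participants have completed all pretreatment assessments". On their number it says "The study will include up to 18 groups each run in succession", with enough recruited "in order to have 3-5 participants beginning each group".

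**The concern.** Routine GEE output rests on a large-sample sandwich variance and a normal or chi-square reference. Both are optimistic when independent units are few, and a joint test with several degrees of freedom suffers more than a single contrast.

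Here the number of units depends on a choice the plan leaves open. There are 60 if the participant is the cluster, which ignores that groups were randomized. There are 12-18 if the group is the cluster, which respects the design but leaves few units. The pilot exists to produce preliminary effect sizes for a larger trial, and the same variance sets the intervals around them. Intervals that are too narrow make the inputs to that trial look firmer than they are.

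**Working it through.** The plan states no significance level, power or error rate, so there is no figure of its own to reproduce.

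**Inputs from the documents.** 60 participants, 30 per arm; five weight assessments; groups randomized, at most 18, with 3-5 starters. The number of groups is 60/5 = 12 to 60/3 = 20, capped at 18, hence 12-18. The main analysis imputes missing values singly, so all 60 stay in with complete data.

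**Assumptions.** Nominal two-sided 5%; categorical time, so Group x Time for weight has (5 - 1) x (2 - 1) = 4 df; normal outcomes; equal-sized clusters; group ICC 0 or 0.05. Simulations used a within-person correlation of 0.8 or 0.9. In the closed form below this correlation drops out.

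**Joint 4-df test, uncorrected.** With K clusters split equally between arms, the sandwich variance averages (K - 2)/K of its true value. The Wald statistic W then satisfies W(K - 5)/(4K) ~ F(4, K - 5). With the chi-square critical value 9.488, the size is P[F(4, K - 5) > 9.488(K - 5)/(4K)].

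| Cluster | K | Threshold | Size | Simulated (8,000 trials) |
|---|---|---|---|---|
| Participant | 60 | 9.488 x 55/240 = 2.174 | 8.4% | 8.5% |
| Group | 18 | 9.488 x 13/72 = 1.713 | 20.7% | 21% |
| Group | 15 | 9.488 x 10/60 = 1.581 | 25.3% | 25% |
| Group | 12 | 9.488 x 7/48 = 1.384 | 33.1% | 34% |

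A check with standard GEE software (800 trials each) gave 9.9%, 19%, 26% and 31%.

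**Participant as cluster, group correlation ignored.** The design effect is 1 + (m - 1) x ICC. At ICC 0.05 it is 1.10 for m = 3 and 1.20 for m = 5. The threshold becomes 2.174/1.10 = 1.977 (size 11.1%) or 2.174/1.20 = 1.812 (size 14.0%). Simulations gave about 11-14%. The ICC must act on changes over time, because a group shift that is constant across visits cancels from Group x Time.

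**Single weight contrast, uncorrected.** The interval width relative to a correct t interval is 1.960 x sqrt((K - 2)/K) / t(0.975, K - 2). The size is P[|t(K - 2)| > 1.960 x sqrt((K - 2)/K)].

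| K | Width ratio | Too narrow by | Size |
|---|---|---|---|
| 60 | 1.960 x 0.983/2.002 = 0.963 | 4% | 5.9% |
| 18 | 1.960 x 0.943/2.120 = 0.872 | 13% | 8.3% |
| 12 | 1.960 x 0.913/2.228 = 0.803 | 20% | 10.4% |

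**Does a correction restore 5%?**
- Mancl-DeRouen variance with F on 4 and K - 2 df, groups as clusters: 7.5% at 18 groups, 8.3% at 15 and 10.4% at 12. This is not enough for the joint test.
- Hotelling-type F on 4 and K - 5 df, groups as clusters: 4.8-5.1% with no group effect, and 4.4-6.0% across all runs.
- Corrected F with the participant kept as cluster: 8.6-10.3% at ICC 0.05 and 11-15% at ICC 0.10. A correction cannot replace the right clustering unit.

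**Abstinence.** The corresponding test over the three post-quit follow-ups rejected 4-5%.

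**The case against.** A reader might infer that the plan uses an uncorrected sandwich variance and that its weight test therefore has an error rate well above nominal. The documents do not support that. They name no variance estimator, and the result depends on the test form. A generalized score test is also ordinary GEE practice, and its statistic is W/(1 + W/K). Its 4-df size is 4.7% at K = 60, 3.4% at K = 18 and 1.6% at K = 12, so it is not inflated.

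The 4-df figures also need categorical time and a joint test. If change from baseline is modelled at four visits, the interaction has 3 df and the participant-level size is 7.5%. With linear time it is a single-contrast problem. The 20-34% range arises only if the analyst clusters on groups, which the plan does not say.

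Finally, effect-size intervals come from single contrasts, not from a joint p-value. At participant level with no group effect those intervals are only about 4% too narrow, point estimates are unaffected, and significance is disclaimed.

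All of this stands and limits the claim to under-specification. It does not remove the point. The disclaimer covers tests, not the precision reported around the effect sizes. The only route to a near-nominal single contrast without correction treats participants as independent, although groups were randomized.

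**Conclusion.** The concern holds as a gap in specification for the weight analysis. Under usual Wald-type inference the joint test would run at about 8.5-9% with participants as clusters and no group effect, about 11-14% at a group ICC of 0.05, and about 20-34% with 12-18 groups as clusters. For a single contrast the rates are about 6% and 8-11%, with intervals about 4% and 13-20% too narrow.

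These figures rest on an assumed 5% level, categorical time, complete normal data and, where used, an assumed ICC. None of these is a document figure except complete data, which follows from the single imputation. It would go too far to extend the point to abstinence, or to read it as a forecast of false confirmatory claims, since the plan makes none. The practical consequence is overstated precision around the weight effects carried forward to the larger trial.

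**What to change.** In the Data Analysis Plan:

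- Name the treatment group as the GEE clustering unit, and state the working correlation and whether time is categorical.
- Use a small-sample corrected sandwich variance (for example Kauermann-Carroll), with t intervals for single contrasts.
- Use a Hotelling-type F for the joint Group x Time test. Base the denominator degrees of freedom on the number of groups (K - 5 for the 4-df weight test). Mancl-DeRouen with F on K - 2 df is not sufficient there.
- For weight, a mixed model with a treatment-group random effect and Kenward-Roger degrees of freedom is an alternative. Without the group effect it would not address the problem.

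The cost is a sentence or two and a software setting; no new data are needed. Intervals for single weight contrasts become about 15% wider at 18 groups (1/0.872 = 1.147) and 25% wider at 12 (1/0.803 = 1.245) than uncorrected group-level intervals. That extra width is uncertainty the uncorrected intervals would leave out.
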